## 18.6 Version 2.0 (30/09/2014) – Minor Amendment

Page Number	Section	Change
Throughout	Header	Updated to reflect version change
Throughout	N/A	'MCRN CTU' changed to 'CTRC' or 'MC CTU' as appropriate
Throughout	N/A	References to "Roland-Morris scale" – 'scale' amended to 'score'
6-8	Table of Contents	Amended to reflect changes in protocol
9	Glossary	Addition of 'CT' and 'XR' definition
10	1	Inclusion criteria: 
 
- removal of 'disabling' from "newly diagnosed disabling sciatica..."
 
- addition of 'and able' to "patient willing to give consent"
 

10	1	Exclusion criteria: 
 
- Addition of "Sciatica presentation for longer than 6 months"
 
- Addition of 'and/or injection' to "...contraindication for surgery"
 
- Addition of "Pregnancy" as a specific exclusion criterion
 

12	1	Schematic of Study Design: 
 
- Addition of EQ-5D-5L at Screening, 18, 30, 42 and 54 weeks
 
- Addition of Return to Work at 18 and 54 weeks
 

18	4.3	Text edited for clarity
19	5.1	Point a) removal of 'disabling' from "newly diagnosed disabling sciatica..."
19	5.1	Point c) "Symptoms" changed to "Severe leg pain"
19	5.1	Points g) and h) added to align with Section 1
19	5.2	Point b) addition of 'spinal' and 'same intervertebral disc' for clarification
19	5.2	Point f) '12 months' corrected to '6 months' in line with Inclusion Criteria
19	5.2	Point i) "Any contraindication for injection" added
19	5.2	Text added to describe assessment of contraindication as per routine care
19	5.3	Minor text amendments for clarification
23	7.2	Addition of an example of an acceptable treatment regimen
23	7.2	Addition of text regarding repeat injections to clarify that repeat injections for Arm A patients are acceptable as per local policy and that data are recorded
24	7.4	Section formatting - 7.4 Cross Over Between Trial Treatments
24	7.4	Minor text amendments to clarify crossover and describe process if participants receive further treatment for sciatica
25	8	Typographical error "retuned" removed
26	8.1	Table 1: 
 
- Addition of EQ-5D-5L to 'Procedures' list
 
- Addition of Unscheduled Visits to the schedule
 

27	8.2	Outcome measures defined as points i) – ix)
27	8.4.1	Correction - EQ-5D-5L not required at treatment visit
27	8.4.1	Clarification - Questionnaires to be returned directly to CTRC
31	9.5.2	Clarification of timelines for IDSMC meetings
32-41	10	Various minor text changes throughout to clarify section
634	10.4	Table 3 events split into A and B for clarity
34-35	10.4-10.6	Change 'table 3' to 'Table 3'
34	10.4	'Drug' removed from "Adverse Drug Reaction" so that AE definition covers reactions to surgical intervention
35	10.6	Typographical error 'Table X' to 'Table 3'
36	10.2	Hyperlink error removed – replaced with '10.1'
36	10.6	Figure 1 updated to refer to Table 3 and clarify reporting procedures for TFESI arm
37	10.6	Figure 2 updated to refer to Table 3 and clarify reporting procedures for surgical arm
37	10.7	Addition of 'Site' to define "Responsibilities – Investigator"
38	10.7 ii	Update to trial co-ordinator telephone number
38	10.7 vi	vi unbolded
41	11.2	Addition of specific REC details
43	12	Addition of CTA and EudraCT detail
45	13.2	Addition of 'Screening Log' and 'Informed Consent' as source documents
46	13.4	Removal of reference to unblinding as NERVES is not a blinded trial

## **18.7 Version 1.0 (27/06/2014)**

Original Approved version.

## **20 DOCUMENTS SUPPLEMENTARY TO THE PROTOCOL**

The following supplementary documents accompany the protocol and are separately updated and version controlled:

- Patient Information Sheet and Consent form (PISC)
- Patient Questionnaires
- Participating centres list
- GP letter

## 1. Change Control

Protocol version	Updated SAP version no.	Section number changed	Description of change	Date changed
V7.0	2.0	17.4.1.1	Addition of details explaining how to derive questionnaire completion dates and when to exclude patients from the analysis.	24/06/2019
V7.0	2.0	17.4.5.2	Updated analysis details. After undertaking blind review on the data, the Likert score was found to be non-normal and therefore a Mann-Whitney U test will be carried out rather than the originally planned T-Test.	24/06/2019
V7.0	2.0	19	Added in additional analysis details.	24/06/2019
V7.0	2.0	20.2	Additional safety details.	24/06/2019
V7.0	2.0	17.4.2.1, 17.4.3.1, 17.4.4.1, 17.4.6.1, 17.4.7.1	Addition of details explaining how to derive missing questionnaire completion dates.	24/06/2019

#### 4. List of abbreviations and definitions of terms

AR	Adverse reaction
CRF	Case report form
ODQ	Oswestry Disability Questionnaire
IDSMC	Independent Data and Safety Monitoring Committee
COMI	Core Outcome Measures Index
RCT	Randomised Control Trial
SAE	Serious adverse event
TFESI	Transforaminal Epidural Steroid Injection
PID	Prolapsed Intervertebral Disc
QOL	Quality Of Life
CTRC	Clinical Trials Research Centre
QALY	Quality Adjusted Life Year
EudraCT	European Union Drug Regulating Authorities Clinical Trials

## 5. Statement of Compliance

This Statistical Analysis Plan (SAP) provides a detailed and comprehensive description of the pre-planned **final** analyses for the study “NErve Root Block VErSUS Surgery (NERVES)”. The planned statistical analyses described within this document are compliant with those specified in brief within the NERVES protocol version 7.0 dated 25/10/2017.

This study is carried out in accordance with the World Medical Association Declaration of Helsinki (1964) and the Tokyo (1975), Venice (1983), Hong Kong (1989) and South Africa (1996) amendments and will be conducted in compliance with the protocol, Clinical Trials Research Centre (CTRC) Clinical Trials Unit (CTU) Standard Operating Procedures (SOPs) and EU Directive 2001/20/EC, transposed into UK law as the UK Statutory Instrument 2004 No 1031: Medicines for Human Use (Clinical Trials) Regulations 2004.

These planned analyses will be performed by the trial statistician.

This study is a clinical trial of a medicinal product and is registered on the European Union Drug Regulating Authorities Clinical Trials (EudraCT) database. The statistical analysis plan has been developed to support the posting of results on the EudraCT system. This is a regulatory requirement which should be fulfilled within 6 months after the end of the study as defined within the clinical trial protocol.

The results of the final analysis described within this statistical analysis plan will be contained within a statistical analysis report. This report will be used as the basis of the primary research publications according to the study publication plan.

All analyses are performed with standard statistical software (SAS version 9.3 or later). The finalised analysis datasets, programs and outputs will be archived following Good Clinical Practice guidelines and SOP TM021 Archiving procedure in CTRC. The testing and validation of the statistical analysis programs will be performed following SOP ST001: Statistical Analysis and Reporting.

## 6. Background and Rationale

The rationale for the trial is outlined in the protocol. To summarise, both epidural steroid injections and surgical procedures are currently being used to remove herniated lumbar disc prolapses for sciatica. There currently exists no care pathway in the NHS that suggests any particular treatment and no comparison between surgical microdiscectomy and transforaminal epidural steroid injection exists. The trial is needed as potential health and economic gains are unlikely to be realised without robust evidence from an RCT. Clear evidence is required on the effectiveness and cost-effectiveness of Transforaminal Epidural Steroid Injection (TFESI) and surgical microdiscectomy.

## 7. NERVES Study Objectives

The objective of this trial is to compare the clinical effectiveness of TFESI for acute sciatica secondary to prolapsed intervertebral disc (PID) and surgical microdiscectomy.

The secondary objectives are:

1. To compare the cost effectiveness of TFESI and microdiscectomy for the treatment of sciatica secondary to PID.
2. To compare quality of life (QOL) outcomes for both treatments.

## 8. Investigational Plan and Study Design

### 8.1. Overall study design and plan- description

NERVES is a two-arm, multi-centre, phase III, randomised trial comparing the clinical and cost effectiveness of trans-foraminal epidural steroid injection to surgical microdiscectomy for the treatment of chronic radicular pain secondary to prolapsed intervertebral disc herniation. The trial includes an internal pilot involving two centres (Liverpool [Walton Centre] and Manchester [Salford Royal]), with an expected recruitment of 30 participants over 6 months. Full details can be found in section 9 of the protocol.

### 8.2. Treatments studied

The two treatments studied in NERVES are Transforaminal Epidural Steroid Injection (TFESI) and Surgical Microdiscectomy.

Dosing and administration details can be found in section 7 of the protocol.

### 8.3. Treatment compliance

Compliance with the randomised study intervention will be monitored by the CTRC through completion of case report forms at site recording the intervention given and the allocation provided by the online randomisation system. Any deviations from the randomised intervention will be explored with site.

During the follow-up patients may require further clinical intervention, which is permitted without the patient having to withdraw. Details of the treatment received and the reason for treatment will be collected. If patients crossover prior to receiving their initial treatment allocation then this should be recorded, with a reason, on the CRF "Form 3: Treatment Form".

The number of patients who start on either treatment (arm A or B) and go on to receive the alternative treatment should be reported in a way that shows:

- The number of patients who started on TFESI and switched to surgical microdiscectomy
- The number of patients who started on surgical microdiscectomy and switched to TFESI
- The number of patients who were allocated to and received TFESI only
- The number of patients who were allocated to and received surgical microdiscectomy only
- The number of injections received by i) patients on the TFESI treatment only, and ii) patients receiving surgery and TFESI

### 8.4. Patient population studied

148 males and females between the age of 16 and 65, who present with sciatica that fail to respond to at least one form of non-operative treatment will be entered into NERVES. Those patients who have a serious neurological deficit, have not attempted any form of conservative treatment, are pregnant, have had previous spinal surgery at the same intervertebral disc and have a contraindication for surgery and/or injection are excluded.

### 8.5. Inclusion criteria

The inclusion criteria can be found in section 5 of the protocol.

### 8.6. Exclusion criteria

The exclusion criteria can be found in section 5 of the protocol.

### 8.7. Removal of patients from therapy or assessment

Due to the nature of both treatment arms removal of patients from therapy is not possible.

### 8.8. Consent process

Consent will be obtained after the investigator has explained the research study to the participant, emphasising that participation in the trial is voluntary and that the participant may withdraw at any stage of the trial for any reason. Consent will be sought at the initial clinical visit before randomisation.

### 8.9. Blinding

NERVES is an open label trial and the investigators and patients will not be blind to allocated treatments.

### 8.10. Method of assignment to treatment

Full details of the randomisation procedure can be found in section 6.3 and 9.2 in the protocol. Participants are randomised to treatment groups in a ratio of 1:1 using an online web randomisation system. Randomisation will be stratified by centre.

### 8.11. Sequence and duration of all study periods

A schematic of the study design can be found in section 1 of the protocol. Details of follow-up visits can be found in section 8.1.

To summarise this information, patients presenting with sciatica will be screened using inclusion and exclusion criteria. Once the patient has been assessed as eligible, consent will be sought. The patient is then entered into NERVES and randomised to either transforaminal epidural steroid injection or microdiscectomy and the treatment is administered. Participants will be asked to complete the ODQ, modified Roland-Morris outcome score, core outcome measures index, EQ-5D-5L and numerical rating score for leg and back pain at baseline, 18, 30, 42 and 54 weeks after randomisation.

### 8.12. Schedule of assessments

A full schedule of trial assessments and timeline of data collection can be found in section 8.1 of the protocol.

## 9. Listing of Outcomes

### 9.1. Primary outcome

The primary outcome is the Oswestry Disability Questionnaire (ODQ) at 18 weeks after randomisation (approximately 3 months post treatment).

### 9.2. Secondary outcomes

The secondary outcomes are:

1. ODQ at 30, 42 and 54 weeks after randomisation.
2. Numerical rating scores for leg pain at baseline, and at 18, 30, 42 and 54 weeks after randomisation.
3. Numerical rating scores for back pain at baseline, and at 18, 30, 42 and 54 weeks after randomisation.
4. Likert Scale to assess patient treatment satisfaction at 54 weeks after randomisation.
5. Modified Roland-Morris outcome score for sciatica at baseline, and at 18, 30, 42 and 54 weeks after randomisation.
6. Core Outcome Measures Index (COMI) at baseline, and at 18, 30, 42 and 54 weeks after randomisation.
7. Work status (return to work and work days lost if applicable).
8. Cost-effectiveness, expressed as the incremental cost per quality-adjusted life-year (QALY) based on the EQ-5D-5L.

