### **4.2 Secondary Endpoint(s)**

- a. ODQ at 30, 42 and 54 weeks after randomisation
- b. Numerical rating scores for leg pain at baseline, and at 18, 30, 42 and 54 weeks after randomisation
- c. Numerical rating scores for back pain at baseline, and at 18, 30, 42 and 54 weeks after randomisation
- d. Likert Scale to assess patient treatment satisfaction at 18, 30, 42 and 54 weeks after randomisation
- e. Modified Roland-Morris outcome score for sciatica at baseline, and at 18, 30, 42 and 54 weeks after randomisation
- f. Core Outcome Measures Index (COMI) at baseline, and at 18, 30, 42 and 54 weeks after randomisation
- g. Work status (return to work and work days lost if applicable)
- h. Cost-effectiveness, expressed as the incremental cost per quality-adjusted life-year (QALY) based on the EQ-5D-5L

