**Table 3: Trial Assessments**

Procedures	Screening / Baseline (T = 0)	Follow-Up Schedule					Unscheduled visits 
		Intervention T=6 weeks 	Time Point T = 18 weeks	Timepoint T = 30 weeks 	Timepoint T = 42 weeks 	Timepoint T = 54 weeks	
Signed Consent Form	X 						
Assessment and Confirmation of Eligibility Criteria	X 						
Review of Medical History	X 						
Review of Concomitant Medications	X 	X	X			X	
Oswestry Disability Questionnaire	X 		X	X 	X 	X	
Health Economic Assessment	X 	X	X	X 	X 	X	
EQ-5D-5L	X 		X	X 	X 	X	
Numerical rating score for leg and back pain	X 		X	X 	X 	X	
Modified Roland-Morris outcome score for sciatica	X 		X	X 	X 	X	
Core Outcome Measures Index (COMI)	X 		X	X 	X 	X	
Study Intervention		X					
Pregnancy Assessment	X	X	X			X	X
Physical Examination	X 		X			X	
Treatment satisfaction (Likert scale)			X	X	X	X	
Return to work			X			X	
Assessment of Related Adverse Events		X	X			X	X
Assessment of additional interventions given to the participant during the trial period			X			X	X 
Telephone follow up of non-responders				(X) 	(X) 		

(X) – As indicated/appropriate.

 Completed prior to randomisation

 Treatment is expected to occur within 6 weeks of randomisation and no later than 12

 Patient is not required to attend clinic at 30 and 42 weeks; Questionnaire posted to the participant by the trial site and posted back to the CTTC by the patient

 Telephone follow up will typically follow one week after initial issue of questionnaire

 Additional visits for further treatment (e.g. TFESI or surgery) may occur as part of routine practice

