## 8.2 Procedures for assessing Efficacy

Efficacy of the trial treatments will be measured through the period of the trial using a number of outcome measures:

- i. Oswestry Disability Questionnaire (ODQ) at 18 weeks after randomisation (approximately 3 months post treatment)
- ii. ODQ at 30, 42 and 54 weeks after randomisation
- iii. Numerical rating scores for leg pain at baseline, and at 18, 30, 42 and 54 weeks after randomisation
- iv. Numerical rating scores for back pain at baseline, and at 18, 30, 42 and 54 weeks after randomisation
- v. Likert Scale to assess patient treatment satisfaction at 18, 30, 42, 54 weeks after randomisation
- vi. Modified Roland-Morris outcome score for sciatica at baseline, and at 18, 30, 42 and 54 weeks after randomisation
- vii. Core Outcome Measures Index (COMI) at baseline, and at 18, 30, 42 and 54 weeks after randomisation
- viii. Work status (return to work and work days lost)
- ix. Cost-effectiveness, expressed as the incremental cost per quality-adjusted life-year (QALY) based on the EQ-5D-5L

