## 8.4 Other Assessments

### 8.4.1 Quality of Life

Participants will be asked to complete the following patient reported outcome measures at baseline, 18, 30, 42 and 54 weeks after randomisation; these have been incorporated into a single patient questionnaire booklet (Patient Questionnaire Booklet 1):

- Oswestry Disability Questionnaire
- Modified Roland-Morris outcome score for sciatica
- Core Outcome Measures Index (including Likert scale for treatment satisfaction)
- EQ-5D-5L
- Numerical rating score for leg and back pain

Patient Questionnaire Booklet 1 (to be completed at baseline, week 18 and week 54 week follow up) will be provided to the participant at the scheduled clinic visits and completed in clinic. Resource Use Questionnaire Booklet 2 is to be completed at the treatment visit **before** treatment and will be provided to the participant in pre-op.

Completion of these questionnaires is an important part of the trial. Particular emphasis should be given to [Part 1 of Patient Questionnaire Booklet 1 \(ODQ\)](#) because it is used to collect primary outcome data for the trial. It is therefore crucial that research staff at site offer any

necessary support to participants to ensure the questionnaires are completed correctly and returned to CTRC either by site or by the participant in accordance with the schedule for follow-up. It is estimated that the questionnaires will take approximately 15 minutes to complete and participants should be advised of the extended visit time prior to their appointment.

All questionnaires completed at baseline will be completed after consent has been provided and prior to randomisation.

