#### 17.4.5.2 Analysis

Patient treatment satisfaction scores at 54 weeks will be compared between groups using the Mann-Whitney U test. A blind review of the data was undertaken and the distribution of the Likert score at 54 weeks was found to be non-normal. The mean difference (along with a 95% confidence interval), test-statistic and p-value will be presented. Summary statistics (mean, SD and range) will also be presented for each treatment group.

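### The SAP analyses treatment satisfaction at week 54 only, although the protocol specifies it at 18, 30, 42 and 54 weeks

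*SAP*

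**What the plan says.** Protocol 4.2, item d, gives the endpoint as "Likert Scale to assess patient treatment satisfaction at 18, 30, 42 and 54 weeks after randomisation". Section 8.2, item v, repeats it: "Likert Scale to assess patient treatment satisfaction at 18, 30, 42, 54 weeks after randomisation". In Table 3 the satisfaction row is marked at all four follow-up points. Protocol 8.4.1 places the items in Patient Questionnaire Booklet 1, as part of the "Core Outcome Measures Index (including Likert scale for treatment satisfaction"), and Table 1 makes that booklet compulsory at weeks 18, 30, 42 and 54.

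SAP 9.2, item 4, reads "Likert Scale to assess patient treatment satisfaction at 54 weeks after randomisation". The heading of 17.4.5 has the same restriction, and 17.4.5.2 states: "Patient treatment satisfaction scores at 54 weeks will be compared between groups using the Mann-Whitney U test". It explains that a blind review found the week-54 score to be non-normal, and then specifies the output: "The mean difference (along with a 95% confidence interval), test-statistic and p-value will be presented".

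SAP section 5 asserts: "The planned statistical analyses described within this document are compliant with those specified in brief within the NERVES protocol version 7.0".

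**The concern.** The current protocol and the current SAP disagree on when a named secondary outcome is assessed, and the SAP neither acknowledges nor explains the difference. An analyst working from the SAP would produce nothing on satisfaction at 18, 30 or 42 weeks, although patients are asked the questions at each of those visits.

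Week 18 is the most noticeable loss. It is the primary time point. For leg pain, back pain, Roland-Morris and COMI, the SAP asks specifically for an effect estimate, interval and p-value there (17.4.3.2, 17.4.4.2, 17.4.6.2, 17.4.7.2). Satisfaction is the only patient-reported scale among the secondary outcomes analysed under this SAP with no week-18 comparison. A reader setting the final report against the protocol would find three time points missing without explanation.

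The smaller issue is the pairing in 17.4.5.2. The p-value comes from a rank test and the interval from a comparison of means, so one result could be read as significant by one and not by the other.

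**Working it through.** **1. Time points side by side**

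- Protocol 4.2d: 18, 30, 42, 54.
- Protocol 8.2v: 18, 30, 42, 54.
- Protocol Table 3: 18, 30, 42, 54.
- SAP 9.2 item 4: 54.
- SAP 17.4.5 heading and 17.4.5.2: 54.

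The protocol summary lists satisfaction without time points, so it does not support a restriction. The week-54 wording recurs in the SAP contents list, the outcome list, the section heading and the analysis text, so a single misprint is unlikely.

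Unreported: 4 − 1 = 3 of 4, or 75%.

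**2. Are the items analysed elsewhere?** Satisfaction is the average of COMI questions 6 and 7 (SAP 17.4.5.1). The SAP's COMI outcome uses questions 1 to 5 (17.4.7.1). So questions 6 and 7 at 18, 30 and 42 weeks enter no analysis.

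**3. Is the change recorded?** The SAP change log has one entry for this outcome, the move from a t-test to Mann-Whitney in 17.4.5.2. It mentions no time points. The log covers only the step to SAP version 2.0, so the restriction may date from version 1.0. The conflict with the protocol is the same either way.

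**4. Test against interval.** The documents give no planning figure for satisfaction. For a realistic group size I used the 66 per group in protocol 9.4.2, which reproduces closely:

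- Adjusted SD = 20 × √(1 − 0.49²) = 17.43.
- n = 2 × [17.43 × (1.960 + 1.282) / 10]² = 63.9, so 64 per group (65 with the t distribution), against 66 stated.
- 66 / 0.9 = 73.3, so 74 per group and 148 in total, as stated.

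The score averages two items coded 1 to 5, so it takes (5 − 1) / 0.5 + 1 = 9 values and ties are heavy. Mann-Whitney bears on P(X > Y) + ½P(X = Y), estimated by U / (n₁n₂). The interval bears on the difference in means. I compared the test with a Welch 95% interval (an assumption, since the SAP names no method) in 4,000 simulated trials per scenario, 66 per arm, with assumed distributions:

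- Identical skewed scores (both means 2.12): they disagree on significance in 2.7% of trials.
- Moderate shift (means 1.93 and 2.35): 9.5%.
- Near-equal means with different shapes (2.43 and 2.39): U is significant while the interval includes 0 in 35%.
- Heavier tail in one arm (1.77 and 2.07): the interval excludes 0 while U is not significant in 32%.

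Significant results in opposite directions never occurred. These figures depend on the assumed shapes and do not estimate what this trial will show.

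**5. Choice of matching estimate.** The Hodges-Lehmann shift is the usual companion to Mann-Whitney but suits this score badly. In 3,000 simulated trials per scenario (66 per arm, assumed skewed scores, three scenarios with a true difference, no tie correction), its 95% interval touched or included 0 in 71% to 99% of the trials in which Mann-Whitney was significant. A second set of assumed distributions gave 62% to 100%.

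**The case against.** Week-54 satisfaction is a legitimate question. The protocol allocates only the initial treatment, permits further intervention (7.4) and is pragmatic, and the SAP analyses by intention to treat. Nor is week 18 plainly better: treatment may be given up to 12 weeks after randomisation, so week 18 can fall only 18 − 12 = 6 weeks after it. This stands. The reason to restore the other visits is that the protocol lists them, not that week 54 is uninformative.

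One could also keep week 54 alone and document the departure. That would remove the contradiction, but three specified time points would still go unreported.

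On the interval, a mean difference at about 66 per arm does not need normal scores, and an unnamed method could be a bootstrap. Disagreement is modest in the plainer scenarios. This is why the pairing is only a minor note.

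A reader might go further in three ways that the documents do not support:

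- That this is selective reporting. Nothing shows why week 54 was chosen or that results by arm had been seen. The one logged change followed a blind review.
- That a registered outcome was altered. No registry record is available here. The documents show only a protocol-specified endpoint.
- That up to half the injection arm will have had surgery by week 54, from the 50% criterion in protocol 9.5.1. That is a pilot progression threshold with no week-54 time frame. It is neither a crossover estimate nor a ceiling, since exceeding it prompts review rather than automatic stopping.

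**Conclusion.** The point holds as an undocumented departure from the protocol in a plan that declares itself compliant. Its size is three of four specified time points for one secondary outcome, including the primary time point. This rests on reading the current texts together and needs no numerical assumption. The primary analysis is unaffected.

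The test and interval mismatch is real but minor. The two may differ on significance, by an amount that depends on an unknown score distribution. Nothing found suggests that they would point in opposite directions.

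**What to change.** In SAP 9.2 item 4 and section 17.4.5, restore 18, 30, 42 and 54 weeks and analyse each in the same way, with no multiplicity adjustment, in line with SAP section 12. Record the change in the log so that the compliance statement in section 5 is accurate.

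In 17.4.5.2, either report the probability of superiority with its 95% confidence interval beside the Mann-Whitney test, or use ordinal logistic regression adjusted for centre. The second option also fits protocol 9.6, which expects secondary outcomes to follow methods similar to the centre-adjusted primary model, with logistic regression where suitable. Keep means and SDs as description only, and do not use the Hodges-Lehmann shift on this heavily tied score.

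The cost is a few lines of SAP text and three more runs on data that Booklet 1 is already scheduled to collect. The small downside is three more unadjusted secondary comparisons.
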